Project Title: Preferred Method of Postoperative Follow Up After Pelvic Reconstructive Surgery. (Phone Call versus Clinic Visit): A Non-Inferiority Randomized Clinical Trial

Primary Investigator: [name]
Fellowship Program: University of South Florida
Year: PGY 6

Co-investigators:
[name], DO
[name]
[name]
[name]
[name]

I. Introduction:

Post-operative visits two weeks following reconstructive pelvic surgery is standard practice for our FPMRS division. With a growing number of new patients, scheduled procedures, and established patients, we, like most academic practices, struggle with maintaining an efficient workflow. To provide the best care, it is necessary to evaluate how we can improve patient satisfaction without seeing an increase in complications. Telephone consultations are increasingly being used as a novel approach to supplement or replace traditional outpatient care for various acute or chronic conditions. [1]. A review article published by Car, J and Sheikh, A found that telephone consultations are associated with increased patient satisfaction, less waiting time, and reduced travel costs. They also reviewed studies that both clinicians and patients value the convenience and flexibility offered by telephone consultations. However, amongst physicians dissatisfied with telephone -based care, the concerns cited included inability to confirm diagnosis with an examination and absence of visual cues [2]. Telephone follow up has been favorably evaluated following laparoscopic cholecystectomy, hernia repair, cardiovascular surgery, and

in oncology [2].

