- Patient who did not attend any postoperative follow up visit

C. Interventions and Recruitment:

The recruitment and consenting process will be performed by an FPMRS fellow or an attending physician and will occur in a private patient exam room at the time of the surgical consultation follow up visit. After obtaining informed consent, the women will be randomized to either a two-week postoperative telephone visit or two-week postoperative clinic visit. The preferred contact phone number and mailing address will be confirmed. The patient will also receive a brief outline summarizing the study and what to expect in laymen terms. These visits typically occur during each of the three attending physicians' clinics. The provider will include that the patient is a study patient in the surgery letter. Once the surgical scheduler confirms that the patient has been enrolled and consented, she will open the next sealed randomization envelope revealing the patient's allocated intervention and schedule the patient's two-week postoperative visit accordingly (telephone follow up or clinic follow up). If the patient is randomized to telephone follow up, the surgical scheduler will again confirm the preferred contact number and mailing address.

Concerning the two-week postoperative follow up visit, if the patient is randomized into the telephone follow up group, she will be contacted, at the pre-scheduled date and time, by the urogynecology clinic nurse. The nurse will utilize a scripted series of postoperative questions, which are consistent with questions asked during our standard postoperative clinic visits. The same nurse will conduct the telephone follow up visits in an effort to maintain consistency. An example of the script is attached.

Any patient responses that are not consistent with a usual postoperative course will be escalated to an in person visit. However, these patients will remain in the group, to which they were originally randomized, for research analysis purposes. If a patient cannot be reached at the time of her scheduled telephone visit, a second

telephone call will be attempted during the same week. If there is still no answer, the patient will be scheduled for an in person visit, the time and date of this visit will be left on the patients voicemail. Patient will be excluded from study. Patients who were found to have recovered satisfactorily based on telephone follow up, will have six -week clinic visit.

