Vital signs and physical examination will be deferred for the patients in the telephone follow up group. The clinic visit will entail questions about common postoperative complications (including fever, nausea/vomiting, pain, urinary symptoms, constipation, etc.). As per usual, vital signs and a focused physical examination will be completed at the clinic visit. All clinic visits will be performed by an FPRMS fellow and/or attending physician. At the end of each visit (telephone and clinic) patient will be reminded about postoperative restrictions as outlined in discharge instructions. The length of duration of both the telephone and clinic visits will be recorded by documenting the start and end time. For the clinic visit the start time will be the time patient is documented as “arrived” status in waiting area and finish time when the physician leaves the room. For the telephone visit, the start time will be at the time the patient answers the phone and finish time when phone call ends. Both clinic and telehealth visits will be documented with progress notes in EMR.

D. Randomization

Eligible patients will be randomized to Arm1 or Arm2 (Telephone follow up or clinic follow up). Permuted block randomization with randomly varying block sizes will be used. Generation of allocation sequences will be performed using a random-number table.

E. Concealment of Treatment Allocation:

The allocation sequence will be generated by our statistician who is neither responsible for patient recruitment or outcome assessment. Sequentially numbered opaque sealed envelopes will be used for concealment of treatment allocation.

F. Blinding:

It is not possible to mask clinical staff or participants, as they will be aware of the follow-up care that is being delivered over the telephone or in clinic. As such this is not a blinded study. The surgical scheduler will open the sealed randomization envelope revealing the patient’s allocated intervention and document this in the patients’ chart. The PI will keep the master link matching the patient to the allocated intervention. The PI is also responsible for entering all collected data into a de-identified excel spreadsheet.

VII. Outcomes

A. Primary:

- Comparison of patient satisfaction as determined by completion of a non-validated, treatment non-specific satisfaction questionnaire between the two groups. Survey will be provided at the six-week follow up visit.

B. Secondary:

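### The visit-length outcome includes waiting in the clinic arm only, so it can be reported as patient elapsed time but not as contact time or clinic efficiency

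*Combined protocol and SAP*

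**What the plan says.** Section II.B lists the difference in visit length between telephone and clinic follow-up as a secondary aim. Section VII.B words the matching outcome as minutes on the call set against minutes in clinic follow-up.

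The clocks are defined in section VI.C: "The length of duration of both the telephone and clinic visits will be recorded by documenting the start and end time". The clinic clock starts when the patient is marked as having arrived, "status in waiting area and finish time when the physician leaves the room". For calls: "For the telephone visit, the start time will be at the time the patient answers the phone and finish time when phone call ends".

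The staff differ as well. In the telephone arm "she will be contacted, at the pre-scheduled date and time, by the urogynecology clinic nurse"; for the other arm, "All clinic visits will be performed by an FPRMS fellow and/or attending physician".

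The Introduction gives two motives that bear on time. One is the patient's: a cited review found that "telephone consultations are associated with increased patient satisfaction, less waiting time, and reduced travel costs". The other is the clinic's: "we, like most academic practices, struggle with maintaining an efficient workflow", followed by the argument that replacing in-person visits would free appointments. Section III states that the telephone visit is safe and efficient.

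No rooming time, provider-entry time or waiting time appears in Methods, Outcomes, Data Collection or Proposed Analyses. The documents do not say whether the electronic record holds such a time.

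**The concern.** The two clocks start at different kinds of event. The clinic clock starts before any care and so includes the wait. The telephone clock starts when the patient picks up, so it has no waiting component. With two time points per visit, nobody can later tell how much of a reported saving was waiting and how much was shorter contact.

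This matters because the plan argues from both the patient's time and the clinic's workflow. Minutes in a waiting room are a cost to the patient, but they are not minutes of clinician time. A reported saving could be taken as evidence for the efficiency part of the hypothesis when some or all of it is waiting. Unless the electronic record happens to hold the missing time, it cannot be recovered after the visit.

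**Working it through.** **The plan's own figures.** The documents give no expected visit length, waiting time or standard deviation, so there is no figure on this point to reproduce. The sample size concerns the primary outcome only, and it does reproduce: (1.960 + 0.842)² × (0.87 × 0.13 + 0.90 × 0.10) / (0.12 + 0.03)² = 7.85 × 0.2031 / 0.0225 = 70.9, that is 71 per group. Visit length does not enter it.

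**What the two clocks measure.** Define:
- W = mean time from arrival to the start of clinic contact
- K = mean clinic contact time, from there to the physician's exit
- T = mean call duration
- C = K − T, the contact-time difference

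The clinic clock gives W + K and the telephone clock gives T. Therefore:

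reported difference = (W + K) − T = C + W

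excess over the contact-time difference = (C + W) − C = W

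This is an identity and holds for any values. It shows that the two constructs differ by W. It does not show how large W is.

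**Illustration.** Every W and C below is assumed, in minutes. Share = W / (C + W).

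| W | C | Reported difference | Share that is waiting |
|---|---|---|---|
| 10 | 15 | 25 | 40% |
| 10 | 5 | 15 | 67% |
| 20 | 10 | 30 | 67% |
| 30 | 5 | 35 | 86% |
| 15 | 0 | 15 | 100% |
| 15 | −5 | 10 | over 100% |

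The first four rows assume that clinic contact is longer than the call. That is plausible, since only the clinic visit includes vital signs and an examination, but the documents give no durations. The range of 40% to 86% is therefore not a bound. In the last row the clinic contact is 5 minutes shorter than the call, yet the reported figure shows the clinic visit 10 minutes longer, so even the sign for contact time could reverse.

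**Can W be recovered from the planned data?** Section VI.C records a start and an end for each visit. These give W + K as one number per clinic patient and T as one number per telephone patient. W and K cannot be separated without a third time point, and no section plans one.

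**The case against.** The case for leaving the outcome alone is good. The protocol states both clocks openly. Arrival to physician exit is a legitimate definition of how long a clinic visit takes, and it fits the outcome as worded in section VII.B. Waiting is a real part of a clinic visit, has no counterpart in the call as timed, and is a burden the Introduction names. No section lists contact time or staff minutes as an outcome. The argument about freed appointments rests on moving the visit out of the clinic, not on a difference in minutes, and section III does not tie the word efficient to this outcome. As a measure of patient burden, the clinic clock even understates, because it omits travel and anything after the physician leaves. The difference in staff belongs to the two follow-up models and is not a timing fault.

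Most of this stands. A reader might infer that the outcome fails to measure visit length at all, or that the clocks bias the comparison towards the telephone. The documents do not support either reading: for patient elapsed time the comparison is usable as defined.

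What the objection does not answer is the efficiency claim. An open definition of elapsed time does not make it a measure of contact time, and the hypothesis says efficient without saying for whom.

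**Conclusion.** The concern holds in a limited form. The planned data support a statement about patient time on site against time on the call, waiting included. They do not support a statement about contact time, staff time or clinic efficiency. The gap between the two constructs is exactly W, minute for minute. Its size is unknown, and the illustrative shares rest wholly on assumed waits and contact times.

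This is a minor point about one secondary outcome. It is worth acting on because visit length is a stated aim, the remedy is cheap, and the missing time may not be obtainable later.

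**What to change.** In section VI.C, add the time the provider enters the room to the times recorded for each clinic visit. Add the rooming time if the electronic record holds it. In Proposed Analyses, specify two labelled rows:

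1. **Patient elapsed time:** arrival to physician exit against call duration, stating that waiting is included and travel is not.
2. **Contact time:** provider entry to exit against call duration, noting that any vital-signs time before provider entry is not counted, and that a nurse makes the calls while a fellow and/or attending conducts the clinic visits.

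Base any efficiency statement on row 2 only. The gap between the rows is the mean time from arrival to provider entry. It is waiting plus any vital-signs time, and should be described that way.

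If no time point can be added, label the outcome as arrival-to-exit against call duration and draw no contact-time or staff-efficiency conclusion.

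The cost is one extra time per clinic visit (none if it can be extracted, or if the outcome is only relabelled) and one more row in a table. The telephone saving in row 2 will probably be smaller than in row 1. The existing comparison is kept.

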- Comparison of adverse events and Emergency Department (ED) visits between the two groups. Will be determined by reviewing the patient's record to identify adverse events as defined below. Informed consent will include consent to obtain outside ED records; as this is standard practice for patients seen in ED during perioperative/postoperative period.
- Actual time spent on phone call during postoperative telephone follow up compared to time spent in clinic follow up measured in minutes.
- Correlation, between groups, of overall patient's satisfaction with subjective measures, complications, demographics, and travel distance.

VIII. Data Collection:

At the initial visit, once eligibility status is determined and consent is obtained, data collection form will include demographics, distance traveled, complications, and number of ED visits, type of surgery performed etc. Also patients will complete three postoperative patient satisfaction questionnaires at the six-week postoperative clinic visit. This will include the Patient Satisfaction Questionnaire (PSQ) 18 Short Form, a validated questionnaire. Also will include the Patient Global Impression of Improvement (PGII), a validated questionnaire. And a three-question survey about patient satisfaction with the postoperative experience, not validated. All six -week visits will be in person. The questionnaires will be completed before the physician interviews the patient. These questionnaires will be stored in a locked filing cabinet and later transferred by the PI to an excel spreadsheet stored on a password-protected computer. Additionally, pertinent medical information will be extracted from the patient's medical chart, de-identified, and transferred to the an excel spreadsheet after surgery by a member of the study team, including socio-demographic data, perioperative and postoperative details, adverse events, and ED visits.

Adverse events are defined based on previous studies [4, 5,]

- bladder injury
- ureteral injury
- bowel injury

- operative estimated blood loss >500mL
- reoperation < 30 days
- hematoma
- pelvic abscess
- vaginal cuff cellulitis
- ileus
- small bowel injury
- transfusion
- pulmonary
- cardiac
- neurological injury
- urinary tract infection (culture proven, urinalysis with presence of leukocyte esterase, nitrites, or blood, symptoms of infection)
- pyelonephritis
- urinary retention (more than 6 week postoperative)
- mesh erosion
- incisional hernia
- wound complication

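### The primary satisfaction survey has no route other than the in-person six-week visit, so a woman who misses that visit has no primary outcome; any resulting bias is of unknown size and direction, and a mailed back-up would be cheap

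*Combined protocol and SAP*

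**What the plan says.** Section VII.A (Outcomes, Primary) fixes when and where the satisfaction survey is given: "Survey will be provided at the six-week follow up visit". Section VIII (Data Collection) repeats this for the full set of instruments, "Also patients will complete three postoperative patient satisfaction questionnaires at the six-week postoperative clinic visit", and adds "All six -week visits will be in person". Neither section, nor section X (Proposed Analyses), describes postal, telephone or electronic completion, a reminder, a time window, or any handling of a missing survey.

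Contact details are available. At recruitment (section VI.C), "The preferred contact phone number and mailing address will be confirmed"; the surgical scheduler confirms them again for the telephone arm. They are not used for the survey.

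Two other provisions bear on the point. The exclusion list in section VI.B ends with "Patient who did not attend any postoperative follow up visit". Section VI.F states "As such this is not a blinded study", so each woman knows which kind of two-week contact she received before she decides whether to return at six weeks.

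Section IX gives 71 women per arm, with no allowance for missing surveys.

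**The concern.** The six-week visit comes after randomisation. If women who do not return differ in satisfaction from those who do, and differ more in one arm than in the other, the difference among attenders is not the difference among all women randomised. The outcome is satisfaction with postoperative care, so a link between satisfaction and returning for that care is plausible. The arms also differ in whether a woman has already been seen in person at two weeks. Both links are inferences; the documents report neither.

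The exclusion wording leaves a second gap. A woman who completes her two-week contact and misses week six could be read as outside the exclusion, because she attended one postoperative visit, or as inside it, because she missed one. On the first reading she stays in the trial with no outcome and no stated handling. On the second she is removed after randomisation. Either way the primary comparison rests on women who came back.

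At stake are the type I error of the non-inferiority claim if loss is selective, and power if it is not. Answers never requested cannot be recovered at analysis.

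**Working it through.** **Inputs from section IX.** Clinic proportion 0.87; telephone proportion 0.75 under the null and 0.90 for power; margin 0.12; one-sided alpha 0.025; unpooled Z test; 71 per arm. As section IX implies, the survey is taken to reduce to satisfied or not satisfied.

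**The plan's own figure.** n = (1.960 + 0.842)² × (0.87×0.13 + 0.90×0.10) / (0.90 − 0.87 + 0.12)² = 70.8, so 71 per arm. With 71 per arm, SE = 0.0535 and power = Φ(0.15/0.0535 − 1.960) = 0.801. The stated figure reproduces, but it counts women who have a survey.

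**Loss at random.** The same formula with 71 × (1 − d) per arm gives power of 0.758 at d = 10% (63.9 evaluable) and 0.734 at d = 15% (60.35 evaluable). There is no bias.

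**Selective loss at the null.** All attendance rates here are assumptions. Let m be the share of telephone women who miss the visit and s the share of those who are satisfied.

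- Telephone proportion among attenders = (0.75 − m·s)/(1 − m).
- Attendance of satisfied women = 1 − m·s/0.75; of dissatisfied women = 1 − m(1 − s)/0.25.
- Chance of claiming non-inferiority = Φ((p_T − p_C + 0.12)/SE − 1.960), with p_T, p_C and SE taken among attenders.

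Scenario 1 (m = 0.10, s = 0.50) implies attendance of 93.3% for satisfied and 80% for dissatisfied women. Scenario 2 (m = 0.15, s = 0.40) implies 92% and 64%. An arm without selective loss has 5% uninformative loss.

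| Where the selective pattern applies | Scenario 1: difference, false claim | Scenario 2: difference, false claim |
|---|---|---|
| Nowhere | −0.120, 2.5% | −0.120, 2.5% |
| Telephone arm only | 0.778 − 0.870 = −0.092, 6.2% | 0.812 − 0.870 = −0.058, 15.7% |
| Both arms, same rates | 0.778 − 0.886 = −0.109, 3.7% | 0.812 − 0.906 = −0.094, 6.1% |
| Clinic arm only | 0.750 − 0.886 = −0.136, 1.4% | 0.750 − 0.906 = −0.156, 0.6% |

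The clinic values come from applying the scenario's attendance rates to 0.87. For example, 0.87×0.933/(0.87×0.933 + 0.13×0.80) = 0.886.

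**Bounds without a selection model.** Suppose attenders show the planning values, 0.90 telephone and 0.87 clinic. The least favourable full-cohort difference counts every missing telephone woman as dissatisfied and every missing clinic woman as satisfied.

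- 10% missing per arm: 0.90×0.90 − (0.87×0.90 + 0.10) = −0.073; the opposite extreme is +0.127.
- 15% missing per arm: 0.90×0.85 − (0.87×0.85 + 0.15) = −0.1245, just beyond the −0.12 margin; the opposite extreme is +0.1755.

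**The case against.** A reader might infer that the plan as written favours a non-inferiority finding, with a false-claim rate as high as 16%. The documents do not support that. They give no attendance rate and nothing to show that arm or satisfaction affects return. The 16% needs 36% of dissatisfied telephone women to miss the visit against 5% of dissatisfied clinic women, a sevenfold gap. A woman already examined at two weeks may equally feel less need to return, which would act in the clinic arm and make the test conservative. Collection is also the same in both arms by design: an in-person visit, with the forms completed before the physician's interview. Giving a survey at a common scheduled visit is an ordinary choice for a single-site trial. All of this stands, and it is why no direction is claimed.

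A reader might also infer that a woman who misses only week six definitely stays in the analysis set. The exclusion wording allows the opposite reading just as well.

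A further objection is that a survey read aloud by telephone brings interviewer-administered answers into a trial that compares telephone with in-person contact. If non-attendance differs by arm, mode of completion will differ by arm too. That also stands, and it is the reason to put self-completion first and to run an analysis restricted to in-clinic responses.

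None of this removes the basic fact: the plan has one collection point and no back-up, although the contact details are held.

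**Conclusion.** The point holds as a cheap, worthwhile improvement to the design, not as a demonstrated bias. It is certain that a woman who misses the six-week visit has no primary outcome under the plan, and that the exclusion wording does not settle whether she is also removed. The size and direction of any bias are unknown. Under the assumed rates, the false non-inferiority rate ranges from about 0.6% to about 16%, depending on which arm loses dissatisfied women selectively. The same pattern in both arms gives about 4% to 6%, and loss unrelated to satisfaction leaves it at 2.5% and lowers power only. If attendance proves nearly complete, the effect is small, but the plan neither states nor secures that.

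**What to change.** Amend VII.A and VIII together. Any randomised woman who does not complete the survey at the six-week visit is sent the same self-completed survey at the mailing address already held, within a fixed window such as two weeks. One telephone attempt follows as a last resort, made by existing staff other than the nurse who conducts the two-week calls. Include these responses in the primary outcome by randomised group, record mode and date of completion, and report completion by arm. Repeat the primary analysis with in-clinic responses only as a sensitivity analysis.

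Reword the last exclusion in VI.B so that missing the six-week visit alone does not remove a woman from the analysis. Reconcile the back-up survey with the other post-randomisation exclusions: Grade 3 complication (VI.B), and telephone-arm women not reached after two calls, for whom VI.C says "Patient will be excluded from study". The text should say whether these women are surveyed and analysed.

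The cost is a short amendment to three sections, postage and a few calls. The downside is that a few responses will arrive later and in a different mode, possibly unequally by arm.

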In the setting of urogynecological procedures, the use of telephone follow up is an area that needs to be studied. There is no known standardization about how postoperative follow up visits are conducted after pelvic reconstructive surgery. There is much variation amongst providers concerning when and how postoperative follow up visits are completed. With the advances in robotic and laparoscopic procedures, hospital length of stay has decreased significantly. We now must examine the benefits of minimally invasive surgery as it relates to postoperative follow up. If in person postoperative visits can be replaced with telephone visits, we can possibly increase patient satisfaction. By allowing the patient to have a postoperative visit in the comfort of her own home, we can save her travel costs and travel time. Additionally, in our practice, the in person postoperative visits can ultimately be replaced with procedures and established patient visits, ultimately allowing for more availability for new patient consultations. By evaluating the use of telephone follow up, versus clinic follow up we will show that patient satisfaction with telephone follow up will be unchanged or improved compared to our standard practices.

II. Objective:

A. Primary Aim(s):

- To determine if patient satisfaction with postoperative care with telephone follow up is non-inferior to clinic follow up.

B. Secondary Aim(s):

- To determine if telephone postoperative follow up is a safe alternative to clinic postoperative follow up visits
- To determine if telephone or clinic follow up visits are preferred based on differing demographics (i.e. age, race, distance traveled, outpatient versus inpatient surgery).
- To determine length of visit differences between telephone and clinic follow up.

III. Hypothesis:

For the standard two-week postoperative visit, follow up telephone calls will be non-inferior to traditional office visits. The telephone visit is a safe and efficient alternative to the in person visit following urogynecological procedures.

a. H_0 Traditional office visits are superior to follow up via telephone calls for two-week postoperative visits.

IV. Interventions:

Scheduled telephone call at the two-week postoperative visit completed by the urogynecology clinic nurse.

V. Study Design:

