- reoperation for complication of surgery
-

IX. Sample Size:

Sample sizes of 71 in Group 1 and 71 in Group 2 achieve 80% power to detect a non-inferiority margin difference between the group proportions of -0.12. The traditional office visit group proportion is 0.87. The Telehealth group proportion is assumed to be 0.75 under the null hypothesis of inferiority. The power was computed for the case when the actual Telehealth group proportion is 0.90. The test statistic used is the one-sided Z test (unpooled). The significance level of the test is 0.025.

X: Proposed Analyses:

Data analyses will be performed at the University of South Florida in Tampa, Fl. Data management and analyses will be conducted using SAS version 9.4 (SAS Institute, Inc, Cary, North Carolina). Subject demographic characteristics such as age, distance traveled, surgical procedures, ED visits will be summarized by standard descriptive statistics (e.g. means and standard deviations or median (range) for continuous variables and percentages for categorical variables. The difference between groups will be compared using the chi-square test or t-test, as appropriate. Logistic linear regression will be used to evaluate independent predictors for patient satisfaction. A p-value <0.05 will be considered statistically significant.

VIII. Confidentiality

At all times, appropriate measures will be taken to protect the confidentiality of all study participants in accordance with HIPAA guidelines. Patients will be approached for recruitment in private patient exam rooms. Once enrolled, all patients will be administered a study ID number starting with 1 and proceeding numerically. A master link between the individual subjects and their study ID number will be stored in a secure location (on a password-protected computer in the Urogynecology Fellows' office). All data collection forms (DCF) and stored patient information will only contain the study ID number. Charts will be reviewed in a secure location at all times. Upon completion of the data collection period, all information will be entered into an excel spreadsheet on a password-protected computer for data analysis.

IX Safety

This a voluntary study. Patients have the right to refuse to participate.

Data and Safety Monitoring

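### The safety outcome compares adverse events and ED visits by arm but not when or where they were recognised, so similar counts alone do not show that complications were recognised on time

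*Combined protocol and SAP*

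**What the plan says.** Section II.B sets a safety aim: "To determine if telephone postoperative follow up is a safe alternative to clinic postoperative follow up visits". Section VII.B answers it with a "Comparison of adverse events and Emergency Department (ED) visits between the two groups". On ascertainment it adds: "Will be determined by reviewing the patient's record to identify adverse events as defined below".

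The chart extraction in VIII (Data Collection) is described as "including socio-demographic data, perioperative and postoperative details, adverse events, and ED visits". It does not mention a date of onset, a date of diagnosis or the contact at which an event was found. Two items in the adverse-event list carry a time (reoperation within 30 days, and retention beyond six weeks). Those times define the event, not when it was recognised.

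Section X gives descriptive summaries and one sentence on comparisons: "The difference between groups will be compared using the chi-square test or t-test, as appropriate". It names no time-based method and does not say whether adverse events are analysed as any versus none or as a count.

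On the two-week contact, VI.C says: "Vital signs and physical examination will be deferred for the patients in the telephone follow up group". It also says: "Patients who were found to have recovered satisfactorily based on telephone follow up, will have six -week clinic visit". The clinic arm has vital signs and a focused examination at two weeks. The call follows a script matched to the clinic questions, and answers outside the usual course lead to an in-person visit, with the woman kept in her randomised arm. VIII makes the six-week visit in person for both arms.

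**The concern.** The randomised difference is the type of surveillance contact at two weeks. Its most direct effect on safety is on when a complication is recognised; its effect on whether one arises in the first place is likely to be small. The planned outcome measures occurrence.

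Take a wound complication that is present at two weeks, causes no answer that triggers escalation, and is found at the six-week visit. It is one event in the telephone arm. The same complication seen on examination at two weeks is one event in the clinic arm. The two are scored alike although the scheduled contacts are four weeks apart.

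This is not the problem of unequal detection, in which one arm's events go unrecorded. It remains even if every event in both arms is found by six weeks. What is at stake is the safety conclusion: similar counts could be read as showing that the call is safe when the plan has not looked at delay.

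**Working it through.** **The plan's own figure.** Section IX (Sample Size) gives 71 per arm for satisfaction, from proportions 0.87 and 0.90, margin 0.12, one-sided alpha 0.025, 80% power and an unpooled Z test.

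n = (0.87×0.13 + 0.90×0.10) × (1.960 + 0.842)² / (0.90 − 0.87 + 0.12)² = 0.2031 × 7.849 / 0.0225 = 70.85, rounded up to 71.

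It reproduces (power 80.1% at 71). It concerns satisfaction and is used here only as the arm size.

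**Assumptions.** The documents give no complication rate and no detection rate. Assume:
- 71 women per arm;
- the same proportion r in each arm with a listed postoperative complication present at two weeks (5%, 10% or 20%);
- a proportion m of these missed on the call (20% or 50%);
- all found by six weeks;
- for this step only, none missed at the clinic visit.

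**Planned outcome.** Expected events are 71r in each arm, whatever m is, so the expected difference is 0. This follows directly from the assumptions and is the point of the illustration: m does not enter the planned comparison. By enumeration, a Pearson chi-square test at 10% versus 10% rejects 5.1% of the time.

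**Late diagnoses.** Expected number in the telephone arm = 71 × r × m. Chance of at least one = 1 − (1 − rm)^71.

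| r | Events per arm | Late, m = 20% | P(≥1) | Late, m = 50% | P(≥1) |
|---|---|---|---|---|---|
| 5% | 3.6 | 0.7 | 51% | 1.8 | 83% |
| 10% | 7.1 | 1.4 | 76% | 3.6 | 97% |
| 20% | 14.2 | 2.8 | 95% | 7.1 | >99% |

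**If the clinic visit also misses some.** With 90% detection in clinic and 50% by telephone, late diagnoses are 71 × 0.10 × 0.10 = 0.7 versus 71 × 0.10 × 0.50 = 3.6 at r = 10%, and 1.4 versus 7.1 at r = 20%. The expected difference in event counts is still 0.

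**What a late-diagnosis comparison could show** (71 per arm, two-sided 5%):

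| Telephone vs clinic, late diagnoses | Power |
|---|---|
| 5% vs 0% (exact enumeration) | 48% |
| 10% vs 0% (exact enumeration) | 93% |
| 10% vs 5% (exact enumeration) | 21% |
| 15% vs 5% (exact enumeration) | 53% |
| 5% vs 1% (r = 10%, detection 50% vs 90%; normal approximation) | 29% |
| 10% vs 2% (r = 20%, detection 50% vs 90%; normal approximation) | 52% |

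The first two rows need no late diagnosis at all in the clinic arm. The third and fourth allow an assumed 5% background of new events after week two in both arms, which is more realistic. The normal approximation in the last two is rough at such small counts.

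**Precision within one arm** (Clopper–Pearson): 0 of 71 has an upper 95% limit of 1 − 0.025^(1/71) = 5.1%; 4 of 71 gives 1.6% to 13.8%.

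**The case against.** **The call has a safeguard.** Its questions match those of the clinic visit, and abnormal answers bring the woman in. Complications with symptoms, such as fever, pain or urinary complaints, may well be caught. Urinary infection is a weak example of something that only an examination finds, because the listed definition rests on culture, urinalysis and symptoms. This stands, and it is why the miss rate is varied down to 20%. It does not cover a finding that produces no unusual answer.

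**Delay is not wholly invisible.** A missed problem that worsens may appear as an ED visit, abscess, pyelonephritis or reoperation. That stands too, although the Grade 3 exclusion in VI.B could remove some of these women. None of these routes separates timely from late recognition.

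**The plan is silent rather than explicit.** The data collection form and call script are not in the supplied text, extraction includes unspecified postoperative details, and an independent urologist reviews safety. Dates may therefore be captured. No stated outcome or analysis uses them.

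**The remedy is imprecise.** Events first diagnosed after a normal two-week contact include new events arising between weeks two and six in both arms; mesh erosion and incisional hernia are on the list. Days to diagnosis among women with an event compares selected subgroups, not randomised arms. Both criticisms stand and limit the remedy to description.

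**A stronger reading to avoid.** A reader might infer from the Introduction that the protocol itself expects this harm and then fails to measure it. The passage, "the concerns cited included inability to confirm diagnosis with an examination and absence of visual cues", reports what a review found among physicians dissatisfied with telephone care in general. It does not mention late recognition, and the protocol's hypothesis is that the call is safe.

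**Conclusion.** The point holds for the secondary safety aim and leaves the primary satisfaction analysis untouched. The planned comparison does not use the time or place of recognition, so similar counts cannot by themselves show that complications were recognised on time.

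The size is illustrative: about 0.7 to 7.1 late-diagnosed telephone women out of 71, against an expected difference in event counts of 0. This rests on assumed complication rates of 5% to 20%, equal in both arms, assumed miss rates of 20% to 50%, and complete detection by six weeks.

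The documents do not support two further inferences. They do not show that telephone follow-up causes late diagnosis, since they contain no detection data. Nor do they support expecting the trial to settle the question if late diagnoses were counted: with a realistic background in both arms, power is about 21% for 10% versus 5% and 53% for 15% versus 5%.

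**What to change.** In VII.B and X:

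1. For each listed postoperative event, record the date of diagnosis, the date of symptom onset if charted, the contact at which it was found, and whether the two-week contact had classed the woman as recovering normally.
2. Report by randomised arm the number and proportion of women with an event first diagnosed after a normal two-week contact, split by where it was found (unscheduled visit, ED, six-week visit), with an exact 95% confidence interval for the difference.
3. Show separately the events charted as present by two weeks, and note that the overall measure includes new events in both arms.
4. Give days from surgery to diagnosis descriptively only.
5. Keep intraoperative events (organ injury at surgery, operative blood loss) out of this table, since the two-week contact cannot affect them.
6. State in X that similar event counts alone do not establish timely recognition, and that the safe-alternative statement will be made alongside this descriptive table.

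**Cost.** A few more items in a chart review already planned. Progress notes for both visit types are in the EMR and consent covers outside ED records. No extra visits, staff or patients are needed, and clinical care does not change. The price is imprecision: even 0 of 71 in one arm leaves an upper 95% limit of 5.1%, and the interval for the difference will be wide. Diagnosis date is only a proxy for onset.
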